11.1 ADVERSE EVENTS

Adverse events will be coded by system organ class and preferred term using the Medical Dictionary for Regulatory Activities, version 22.0 or newer.

An AE will be considered a treatment-emergent adverse event (TEAE) for the study treatment period if the AE meets one of the following criteria:

- The onset date is on or after the first study treatment date.
- The onset date is before the first study treatment date and either:
 - The severity of the event worsened on or after the first treatment date.
 - The event became serious on or after the first study treatment date.

An AE will be considered as a TEAE for a treatment cycle if the AE meets one of the following criteria:

- The onset date is on or after the treatment administration of the cycle but prior to the next cycle administration.
- The onset date is before the treatment administration of the cycle and either:
 - The severity of the event worsened on or after the treatment administration of the cycle.
 - The event became serious on or after the treatment administration of the cycle.

An ocular AE will be defined by the location information on the adverse event page in eCRF.

An overall summary of patient incidences of TEAEs will be presented by event type and event category (ocular or non-ocular). These summaries will include the following:

- All TEAEs
 - Ocular
 - Non-ocular
- Treatment-related TEAEs:
 - Ocular
 - Related to study drug
 - Related to study drug administration procedure
 - Related to SLT laser
 - Non-ocular
- Treatment-related serious TEAEs:

- Ocular
 - Related to study drug
 - Related to study drug administration procedure
 - Related to SLT laser
- Non-ocular
 - Any TEAEs leading to Bim SR implant removal
 - Any TEAEs leading to study discontinuation
 - Deaths

The following non-ocular TEAEs will be summarized by SOC and PT:

- Any non-ocular TEAEs,
- Any treatment related non-ocular TEAEs,
- Any serious non-ocular TEAEs, and
- Any non-ocular TEAEs leading to study discontinuation.

Ocular TEAEs will be summarized by analysis cycle and by treatment eye as described below:

- Any ocular TEAEs by PT
- Any ocular TEAEs by SOC, PT, and severity
- Any treatment related ocular TEAEs by SOC and PT
- Any serious ocular TEAEs by SOC and PT
- Any ocular TEAEs leading to study discontinuation by SOC and PT
- Any ocular TEAEs within two days of study treatment by SOC and PT
 - i.e, Ocular TEAEs that occur within two days from the Bim SR treatment for the Bim SR eye and/or (Bim SR sham for the SLT eye)
- Any ocular TEAEs after two days of study treatment by SOC and PT
 - i.e, Ocular TEAEs that occur after two days from the Bim SR treatment for the Bim SR eye and/or (Bim SR sham for the SLT eye) to next Bim SR/ Sham Bim SR treatment (Bim SR sham for SLT eye)
- SLT procedure related ocular TEAEs by SOC and PT
 - i.e, Ocular TEAEs that occur starting from Day 1, but before the first Bim SR treatment will be summarized.

- Any corneal TEAEs of interest by SOC and PT (Corneal AEs of interest will be identified separately prior to database lock.)
- Any anterior segment inflammation TEAEs of interest by SOC and PT (Anterior segment inflammation AEs will be identified separately prior to database lock.)

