11.0 SAFETY ANALYSES

All safety analyses will be performed using the safety population. Unless otherwise stated, the last non-missing safety assessment before the SLT treatment (Day 1) will be used as the baseline for all analyses of that safety parameter. As indicated in Section 6.4, safety data collected at Screening for eligibility assessment will not be analyzed.

All safety analyses described in the section 11.0 will be performed both Bim SR 10 µg and Bim SR 15 µg.

Ocular safety will be evaluated through; ocular AEs, best corrected visual acuity, visual field examination, specular microscopy, macroscopic iris color assessment, macroscopic conjunctival hyperemia assessment, gonioscopy/angle assessment, biomicroscopy (using a slit lamp), lens assessment, optic disc examination, dilated ophthalmoscopy, pachymetry, and anterior segment-optical coherence tomography.

Non-ocular safety analysis includes non-ocular adverse events (AEs), clinical laboratory results, vital signs (blood pressure, pulse rate and temperature), and pregnancy test results.

Safety analyses will be summarized by study periods. Analysis study periods are defined as follows:

- **During the study:** Date of SLT treatment through Month 24/Exit visit/last study visit available.
- **Analysis Cycle 1:** SLT Treatment date (Day 1) through the second Bim SR administration date – 1. If the second Bim SR administration was not given to a patient, all safety assessments through Month 24/Exit visit/last study visit available will be included in analysis cycle1.
- **Analysis Cycle 2:** Second Bim SR administration date through Month 24/Exit visit – 1.
- **Analysis Cycle 3:** Third Bim SR administration date through Month 24/Exit visit – 1, valid for only Bim SR 15 µg.

All summaries will be based on the first treatment received in each eye (Bim SR or SLT). If a patient who received both SLT and Bim SR in the same eye, safety assessments will be summarized in Bim SR. For non-ocular safety measures, overall summaries will be presented regardless of study treatment. For ocular safety assessments, summaries will be presented for the periods of during the study, Analysis Cycle 1 and Analysis Cycle 2 as shown in Figure 11-1 below.

Figure 11-1 Analysis Cycle Illustration

| Treatment Schedule | Cycles for Safety Data Analyses | |
|--|---------------------------------|------------------|
| | SLT eye | BIM SR eye |
| Day 1, SLT administration | Analysis Cycle 1 | Analysis Cycle 1 |

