12.4 OCULAR ADVERSE EVENT BY FIXED AND FLEXIBLE ADMINISTRATION

Overall and by-cycle ocular adverse event, corneal adverse events, and ocular adverse events leading to implant removal will be analyzed by flexible or fixed dosing regimen subgroup. Other ocular adverse events by the subgroup may be performed on as-needed basis.

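### The by-cycle TEAE criteria for worsened or newly serious events have no end date, so an event with onset before a cycle can be flagged there for a change that came only after a later implant

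*SAP*

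**What the plan says.** SAP 11.1 gives two routes by which an adverse event becomes a TEAE for a cycle.

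- Onset route: "The onset date is on or after the treatment administration of the cycle but prior to the next cycle administration". This is closed at both ends.
- Change route: "The onset date is before the treatment administration of the cycle and either" of two things holds, namely "The severity of the event worsened on or after the treatment administration of the cycle" or "The event became serious on or after the treatment administration of the cycle". Neither has an end date.

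The flag feeds the main ocular safety tables: "Ocular TEAEs will be summarized by analysis cycle and by treatment eye as described below". SAP 12.4 uses it again for the fixed and flexible regimens: "Overall and by-cycle ocular adverse event, corneal adverse events, and ocular adverse events leading to implant removal will be analyzed".

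SAP 11.0 separately defines the analysis periods. Analysis Cycle 1 is "SLT Treatment date (Day 1) through the second Bim SR administration date – 1", or runs to the end of follow-up if there is no second implant. Analysis Cycle 2 is "Second Bim SR administration date through Month 24/Exit visit – 1". Analysis Cycle 3 exists only for 15 µg and starts at the third administration; Analysis Cycle 2 is not shortened to make room for it.

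**The concern.** The change route has the same form as the whole-study TEAE rule just above it in SAP 11.1. There an upper limit is unnecessary, because no later period follows. At cycle level one is needed, and the onset route has it. Without it, a deterioration that followed a later implant is also credited to an earlier cycle in which it did not occur.

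The by-cycle ocular tables are how the trial separates what follows the first implant from what follows the second. The missing limit can only add flags to earlier cycles; it never removes one. At 10 µg, such an event counts in both cycles instead of Cycle 2 alone, so any excess after the second implant would be slightly understated.

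**Working it through.** The plan states no figure here, so there is nothing to reproduce. The check applies the rule as written and with an upper limit to illustrative events.

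**Inputs.** The criteria come from SAP 11.1. Administration days are assumed for illustration: Cycle 1 on Day 1, Cycle 2 at Week 16 (16 × 7 + 1 = 113) and, for three implants, Cycle 3 at Week 32 (32 × 7 + 1 = 225).

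**Formulas.** Let A(k) be the administration day of cycle k, O the onset day, and W the day on which the event first worsened or became serious.

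- Onset route: A(k) ≤ O < A(k+1).
- Change route as written: O < A(k) and W ≥ A(k).
- Change route with a limit: O < A(k) and A(k) ≤ W < A(k+1).

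The last cycle has no A(k+1), so no limit applies there.

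**Results (cycles flagged).**

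| Implants | O | W | As written | With limit |
|---|---|---|---|---|
| 2 | −20 | 60 | 1 | 1 |
| 2 | −20 | 120 | 1, 2 | 2 |
| 2 | 50 | 120 | 1, 2 | 1, 2 |
| 2 | 150 | 160 | 2 | 2 |
| 3 | −20 | 240 | 1, 2, 3 | 3 |
| 3 | 50 | 240 | 1, 2, 3 | 1, 3 |
| 3 | 150 | 240 | 2, 3 | 2, 3 |

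**Reading the table.**

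- Row 2 is the 10 µg problem. For Cycle 1, −20 < 1 and 120 ≥ 1, so the event is flagged as written; with the limit, 120 < 113 fails and the flag drops. Cycle 2 is flagged either way, since −20 < 113 and 120 ≥ 113.
- Row 3 is the ordinary case and is not an error. The Cycle 1 flag comes from onset (1 ≤ 50 < 113) and the Cycle 2 flag from the worsening.
- Row 6 is the additional 15 µg problem. Cycle 1 is right by onset and Cycle 3 by the change; the Cycle 2 flag is spurious.

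**Who can be affected.** The extra flag needs an onset before the earlier cycle's administration and a first change after a later administration. At 10 µg there are at most two cycles, so the event must begin before Cycle 1 treatment. Such events can be on record: Protocol 9.1.1 collects adverse events from consent, and up to 28 days of screening and up to 56 days of washout precede treatment. The event must then stay unresolved and unchanged until the second implant, at Week 16 or later. Patients who never receive a second implant cannot be affected.

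**The case against.** **Analysis Cycle 1 is already bounded.** SAP 11.0 says safety is summarized by study period and ends Analysis Cycle 1 the day before the second administration; 11.1 tabulates by analysis cycle, the term 11.0 defines. Read together, a change after the second implant falls outside Cycle 1. This is the best counter-argument, and it shows what the SAP probably intends. It does not settle the matter: 11.1 is the specific TEAE rule, does not refer to the 11.0 limit, and states a limit for onset only. Two programmers could derive different flags. For a third implant the argument gives no help, because 11.0 does not close Analysis Cycle 2 there.

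**At 15 µg the period definition agrees with the flag.** Under 11.0 a change after the third implant still lies inside Analysis Cycle 2. That stands, and it means that correcting 11.1 alone would leave the two sections with different ends for Cycle 2. They already differ for onset, which 11.1 stops at the next administration.

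**Worsening may be recorded as a new event.** The documents do not say whether a worsening is a dated change on one record or a new record with its own onset. If it is a new record, the bounded onset route applies and the problem disappears. This is a real unknown, but the change route presupposes events that keep an earlier onset date.

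**Treatment comparisons.** A reader might infer a bias between Bim SR and SLT eyes, or between fixed and flexible regimens. The same rule applies to all of them, and the documents do not show a differential effect.

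**Conclusion.** The defect is real and narrow. As written, SAP 11.1 flags an event in an earlier cycle when its onset precedes that cycle's administration and its first worsening or seriousness comes only after a later one. At 10 µg that means pre-treatment events first changing after the second implant. In 15 µg patients with a third implant it also means Cycle 1-onset events first changing after the third, which are added to Cycle 2.

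Two stronger readings are not supported. First, a reader might infer that any event worsening after a later implant is miscounted in an earlier cycle; events with onset in Cycle 1 that worsen in Cycle 2 are correctly in both. Second, a reader might attach a count. Assuming that 5–10% of 160 patients enter treatment with an ongoing ocular event, and that 5–10% of those first worsen after the second implant, gives 160 × 0.05 × 0.05 = 0.4 to 160 × 0.10 × 0.10 = 1.6 events. Neither rate is in the documents, and 160 is too large a base: the second implant is conditional on the retreatment criteria (Protocol 5.9.1.5) for patients under Amendment 6, and some patients discontinue. At 15 µg, SAP 15.0 gives 55 treated patients, but neither document says how many had a third implant.

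The number affected therefore cannot be derived; it is probably very small. The conclusion assumes that the rule is programmed literally and that a worsening stays on the original event record. Only by-cycle counts are touched; whole-study TEAE counts and the efficacy analyses are not. This is a minor correction.

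**What to change.** Make two edits together.

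1. In SAP 11.1, add to both sub-bullets of the by-cycle change route (worsened; became serious) the condition that the change falls before the following cycle's administration, matching the onset route. Leave the whole-study TEAE rule as it is.
2. In SAP 11.0, end Analysis Cycle 2 the day before the third Bim SR administration for patients who had one, so that 11.0 and 11.1 agree.

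The cost is two short wording changes, one date condition in the TEAE derivation and one period end date for the three-implant patients. The existing criteria already require dating the change against the administration, so no new data are needed.

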11.2 VITAL SIGNS

Vital signs (systolic and diastolic blood pressures [mmHg], pulse rate [bpm], and temperature [Celsius]) will be collected at baseline, but will not be analyzed.

11.3 OTHER SAFETY PARAMETERS

Blood and urine samples obtained for the analysis of blood chemistry, hematology, and urinalysis will be reviewed by the investigator or qualified site personnel for any adverse events. Any safety laboratory test results that represent adverse events will be reflected on adverse event eCRF page, and thus will be part of the suggested analyses of AEs. Therefore, laboratory data collected will not be analyzed.

11.3.1 Pregnancy

Pregnancy test results for female patients of childbearing potential will be collected but will not be analyzed or listed.

11.3.2 Best Corrected Visual Acuity

Best-corrected visual acuity (BCVA) at an assessment timepoint is recorded in Snellen equivalent units on eCRF as 20/8, 20/10, 20/12.5, 20/16, ..., or 20/800. An increase in the second number (denominator) in Snellen equivalent unit indicates worsening of VA and a decrease indicates an improvement. For example, change from 20/32 to 20/40 is a worsening of VA by one line, 20/32 to 20/20 (note that 20/25 is in between) is an improvement by 2 lines.

The line change from baseline at each post-baseline evaluation can be calculated using the formula:

$$\text{Line change} = 10 \times [\log_{10}(d_{\text{BL}}/d_{\text{PBL}})]$$

where d_{BL} = denominator of the Snellen equivalent unit at baseline,
 d_{PBL} = denominator of the Snellen equivalent unit at post-baseline

The logarithmic value in the formula above needs to be rounded to the nearest tenth before proceeding to the calculation of the line change. A positive value indicates an improvement, a negative value indicates a worsening, and a zero indicates no change. For example, the line change for a Snellen equivalent unit at baseline of 20/25 followed by a Snellen equivalent unit of 20/80 at a post-baseline visit would be:

Line change = $10 \times [\log_{10}(25/80)] = 10 \times (-0.5)$ (rounded to nearest tenth) = -5 representing a worsening of 5 lines in VA. Note that there are 4 Snellen equivalent units (20/32, 20/40, 20/50 and 20/63) between 20/25 and 20/80, thus moving from 20/25 to 20/80 is a worsening by 5 lines in VA because the denominator has increased.

Summary statistics for the line change from baseline will be presented by visits in each of the following categories: worsening (< -2), no change (≥ -2 and ≤ 2), and improvement (> 2). The data for the largest line change from baseline across follow-up will be summarized for the entire study period (overall) and analysis cycle. The largest line change is defined as the greatest decrease from baseline in the number of lines read during the entire study period for overall summary or within analysis cycle for by-cycle summary.

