6.2 Safety Measures

The following will be collected and recorded on the appropriate eCRF page(s):

Adverse Events: All adverse events, from the moment the patient signs the informed consent form, will be monitored and recorded in the patient's source documents. All events will be reported to Allergan on an adverse event eCRF, including seriousness, severity, action taken, and relationship to study drug. If adverse events occur, the first concern will be the safety of the study patient.

Weight and Height: Weight will be measured in pounds (lb) or kilograms (kg) using a scale. Height will be measured in inches (in) or centimeters (cm). Height and weight will be measured at Screening as part of the demographic data; historical patient information and/or patient reports should not be used for either measurement.

Vital signs: Systolic and diastolic blood pressure and pulse rate will be measured after patients have been at rest (seated) for at least 5 minutes. Body temperature will be measured orally (or with an infrared forehead thermometer) and recorded as $^{\circ}$ F or $^{\circ}$ C.

Blood and Urine Sample Collection: Blood and urine samples will be collected for blood chemistry, hematology panels, and urinalysis by a central laboratory or designated regional facility.

Pregnancy: Females of childbearing potential will have pregnancy tests performed. Pregnancy test kits will be provided by Covance Central Laboratory Services or a designated regional laboratory and will be administered according to the instructions provided with the tests.

Measures of Ocular Safety:

Best Corrected Visual Acuity: Visual acuity tests will be performed at all scheduled visits except on any of the Bimatoprost SR administration days or SLT Administration Day. Manifest refraction using Snellen equivalent with a logMar chart (see Procedure Manual) will be performed at Screening; Baseline; Weeks 12, 24, and 52; and Months 18 and 24/Exit. At all other visits, the visual acuity technician will use the last manifest refraction performed and determine the Snellen equivalent visual acuity using the logMar chart. If there is a 2-line or more reduction in visual acuity from the last best-corrected visual acuity performed, a repeat manifest refraction in both eyes and best-corrected visual acuity will be performed.

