11.3.8 Optic Disc Examination

Optic nerve cup/disc ratio will be evaluated using a 0.0 to 1.0 scale, with larger values indicating more advanced optic nerve damage, thus a reduction from baseline is a considered an improvement. Categorical changes in cup/disc ratio from baseline will be summarized for post-baseline visits. Change from baseline at the follow-up visit (visit value – baseline values) will be categorized as an improvement of 0.2 or more (≤ -0.2), no change (> -0.2 to < 0.2), or a worsening if the ratio increases by 0.2 or more (i.e., change ≥ 0.2). The number and percentage of patients in each category will be summarized by visit and analysis cycle.

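### SAP 11.3.2 tabulates 1- and 2-line acuity losses as no change, so a 2-line loss from baseline is not visible in the by-visit categories

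*SAP*

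**What the plan says.** SAP 11.3.2 defines line change from baseline as 10 times the base-10 logarithm of the baseline Snellen denominator over the post-baseline one. It adds: "The logarithmic value in the formula above needs to be rounded to the nearest tenth before proceeding to the calculation of the line change". On the meaning of the result it says: "A positive value indicates an improvement, a negative value indicates a worsening, and a zero indicates no change". Its one-line illustration is that a "change from 20/32 to 20/40 is a worsening of VA by one line".

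For reporting, line change is summarised by visit in three categories: "worsening (< -2), no change (≥ -2 and ≤ 2), and improvement (> 2"). The section also promises a summary of the largest line change, meaning the greatest decrease, for the whole study and by analysis cycle. It does not say whether that summary uses the same categories. SAP 17.5 adds that all post-baseline assessments go into the data listings.

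Protocol 6.2 has a separate rule for the conduct of the visit: "If there is a 2-line or more reduction in visual acuity from the last best-corrected visual acuity performed, a repeat manifest refraction" and a repeat acuity measurement are to follow.

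**The concern.** The label contradicts the section's own definition. A value of -1 or -2 is a worsening where the measure is defined and no change where it is tabulated. No reason is given for the cut-point.

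The boundary also differs from the SAP's comparable ocular safety categories, which count the threshold value itself. Conjunctival hyperemia (11.3.4) and biomicroscopy findings (11.3.7) count an increase of at least 2 grades. Endothelial cell loss (11.3.5) uses ≥ 10% and ≥ 15%. Cup/disc ratio (11.3.8) calls it "a worsening if the ratio increases by 0.2 or more".

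Visual acuity is a named safety measure for an implant placed in the anterior chamber, and the paired-eye design allows Bimatoprost SR and SLT eyes of the same patient to be compared directly. If the two differ only in the frequency of 2-line losses, the by-visit category table will not show it, and a study report could describe those eyes as unchanged.

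**Working it through.** **1. Reproduce the SAP's example.** From 20/25 to 20/80: log10(25/80) = -0.505, rounded to -0.5, times 10 = -5. This agrees with the SAP, "representing a worsening of 5 lines in VA". Its two other examples also reproduce: 20/32 to 20/40 gives -1, and 20/32 to 20/20 gives +2.

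**2. Which losses fall where.** A logarithm rounded to one decimal and multiplied by 10 is a whole number, so a value below -2 means -3 or lower.

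| Baseline to follow-up | log10 ratio | Line change | SAP category |
|---|---|---|---|
| 20/20 to 20/25 | -0.097 | -1 | no change |
| 20/20 to 20/32 | -0.204 | -2 | no change |
| 20/25 to 20/40 | -0.204 | -2 | no change |
| 20/50 to 20/80 | -0.204 | -2 | no change |
| 20/20 to 20/40 | -0.301 | -3 | worsening |

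**3. Compare with the protocol rule.** Protocol 6.2 measures the drop from the last BCVA, and the SAP measures it from baseline. The two can disagree in either direction:
- 20/20, then 20/25, then 20/32: each step is 1 line, so the rule does not fire, yet the change from baseline is -2.
- 20/25, then 20/20, then 20/32: the last step is 2 lines, so the rule fires, yet the change from baseline is -1 (log10(25/32) = -0.107).

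The sizes are comparable but the quantities are not the same.

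**4. How many losses are affected.** Neither document gives a distribution of line change, so this step rests on assumption. Take line change as normal with mean m and SD s lines, rounded to whole lines. Then:

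- P(loss of 2 or more) = Φ((-1.5 - m)/s)
- P(loss of 3 or more) = Φ((-2.5 - m)/s)
- share of losses of 2 or more labelled no change = 1 - P(3 or more)/P(2 or more)

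| m | s | P(2 or more) | P(3 or more) | Share labelled no change |
|---|---|---|---|---|
| 0 | 1 | 0.067 | 0.006 | 91% |
| 0 | 2 | 0.227 | 0.106 | 53% |
| 0 | 4 | 0.354 | 0.266 | 25% |
| -2 | 1 | 0.691 | 0.309 | 55% |
| -4 | 1 | 0.994 | 0.933 | 6% |

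The share is large when changes are small and centred near zero. It is small when losses are large or widely spread.

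**The case against.** The strongest reply is that the categories are coherent as they stand. They are symmetric, exhaustive and do not overlap, and a cut at 3 lines is defensible for a measure that varies from visit to visit. That stands: nothing in the SAP shows that a 2-line cut was intended, so the boundaries cannot be called an error of direction. It does not explain the no-change label or the missing rationale.

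A reader might infer that the SAP contradicts the protocol. The documents do not support this. The protocol rule has a different reference (the last BCVA) and a different consequence (a re-measurement), and the protocol nowhere names 2 lines as a safety endpoint. What remains is narrower: a drop large enough to prompt a re-check has no row of its own when it is measured from baseline.

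A reader might also infer that most acuity loss will be reported as none. That does not follow either. The share depends on an assumed distribution, and the largest-decrease summary, the listings and the adverse event tables by eye (SAP 11.1) are further routes by which a 2-line loss may appear. These are only partial cover. The format of the largest-decrease summary is open, listings do not compare the eyes, and an adverse event depends on being reported as one.

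Finally, with mean change 0 there are as many 2-line gains as losses, so the mean-0 rows describe scatter and show no hidden harm. That is correct. They show how much the category conceals, not that a safety signal exists.

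**Conclusion.** The point holds in limited form. By the SAP's own formula, losses of 1 and 2 lines are placed in a category labelled no change, against the same section's statement that only zero is no change. This part needs no assumption. As a result, a 2-line loss from baseline cannot be distinguished in the by-visit three-category comparison of Bimatoprost SR and SLT eyes. It may be seen only in a largest-decrease summary of unstated format, in listings, or through adverse event reporting.

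The size is not known. The figures of 91%, 53% and 25% of losses of 2 lines or more rest on an assumed rounded normal distribution with mean 0 and SDs of 1, 2 and 4 lines, and the share falls further if average loss is large. This is a weakness in one descriptive safety table. It affects no hypothesis test.

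**What to change.** In SAP 11.3.2, replace the three categories with five: ≤ -3, -2, -1 to +1, +2 and ≥ +3 lines. Label each by its range, so that the middle one is not called no change. Present them by eye, both by visit and for the largest decrease (overall and by analysis cycle), and state that format in the text. This keeps the 3-line view and makes 2-line changes visible in both directions without choosing between the two cut-points.

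The cost is a short edit to the SAP and a few extra table rows from data already collected. Two-line losses will appear as a separate, less favourable count in both eyes. The primary analysis is unaffected.
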